12.4 Best response and objective response rate (ORR)

For patients with all disease sites assessed every evaluation period, the best response will be defined as the best objective status as measured according to section 12.2/12.3. If the response does not persist at the next regular scheduled MRI/CT, the response will still be recorded based on the prior scan, but will be designated as a non-sustained response. If the response is sustained, e.g. still present on the subsequent MRI/CT, it will be recorded as a sustained response, lasting until the time of tumor progression.

The objective response rate (ORR) is defined as the portion of patients with a best response of CR plus PR according to section 12.2/12.3 divided by the total number of patients included in the study.

12.5 Neurological exam

Although not used for determining response, it is useful to evaluate changes in the neurological exam compared to the previous exam. The following scale may be used:

+2	Definitely better
+1	Possibly better
0	Unchanged
-1	Possibly worse
-2	Definitely worse

Additionally the participant will be evaluated for neurologic functioning by the investigator and according to the NANO scale (). Assessments will be performed at baseline and will each treatment response assessment (every MRI visit). The NANO is an objective, quick, user-friendly and quantifiable evaluation of nine major domains for subjects with brain tumors. The domains include: gait, strength, ataxia, sensation, visual field, facial strength, language, level of consciousness, behavior and overall. Each domain is rated on a scale of 0 to 3 where 0 represents normal and 3 represents the worst severity. A given domain should be scored non-evaluable if it cannot be accurately assessed due to pre-existing conditions, co-morbid events and/or concurrent medications. The evaluation is based on direct observation/testing performed during routine office visits. The NANO scale will be completed by the investigator or designated study physician prior to day 1 cycle 1 (baseline) and then with each MRI).

12.6 Performance status

Participants will be graded according to Karnofsky Performance Status Scale (KPS) (Appendix 6).

12.7 Overall survival time (OS)

Overall survival time (OS) is defined as the time from treatment start to the date of death due to any cause. Patients not known to have died will be censored at the time of their last available assessment or at the analysis cut-off whichever comes earlier.

OS will be described using Kaplan-Meier curves with appropriate summary statistics.

12.8 Progression-free survival (PFS)

Progression-free survival (PFS) is defined as the time from the date of treatment start to the date of the first documented PD or death due to any cause. If a patient is not known to have progressed or died at the date of the analysis cut-off or when he/she receives any further anti-cancer therapy, PFS is censored at the time of the last tumor assessment before the cut-off date and before the anti-cancer therapy date. PFS will be based on the investigator's assessment of MRI, CSF studies and clinical presentation.

PFS will be described using Kaplan-Meier curves with appropriate summary statistics. Additionally, we will report PFS at 12 weeks (PFS12w), PFS at 24 weeks (PFS24w) and at 48 weeks (PFS48w).

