10.0 EVALUATION DURING TREATMENT/INTERVENTION

10.1 General Requirements

Table 6 describes the required procedures. All procedures may increase in frequency if clinically indicated or oriented following a toxicity/adverse event.

A complete history, vital signs (including blood pressure, pulse, respiratory rate, temperature, weight and height), physical and neurological examination (to include documentation of the patients Karnofsky performance status (Appendix 6) and NANO score as well as a serum pregnancy test for women of childbearing potential will be performed on day 1 (+/- 4 days) of each cycle.

Neuro-imaging (including contrast-enhanced MRI/CT brain and total spine) and/or CSF collection (for patients with CSF disease; through Ommaya or spinal tap; including cytology) will need to be performed on all patients on day 1 cycle 3, and each additional odd numbered cycle (+/- 4 days). Imaging will include only the side of active disease (MRI brain for patients with brain disease; MRI total spine for patients with intraspinal disease; MRI brain and total spine for patients with brain and spine disease as well as leptomeningeal disease) or sides suggested by new neurologic symptoms and signs. All MRI imaging will included MR perfusion . If MRI spectroscopy is additionally performed, we will collect the additional data.

CBC with differential, platelets, sodium, potassium, calcium, AST, ALT, alkaline phosphatase, total bilirubin, fasting plasma glucose, creatinine, will need to be performed at day 1 and day 15 of each cycle and at the end of the treatment (+/- 4 days).

Amylase and lipase need to be assessed at the end of the treatment (+/- 4 days).

Chest X-ray and 12-lead ECG need to be done every other cycle starting at day 1 of cycle 3 (+/- 4 days)

Participants need to complete the PHQ-9 and GAD7 self rating mood scale (see Appendix 6).at day 1 and day 15 of cycle 1 and 2. On each consecutive cycle only on day 1 and at the

**MEMORIAL SLOAN-KETTERING CANCER CENTER
IRB PROTOCOL**

IRB#: 14-177 A(5)

end of treatment (+/- 4 days). Questionnaires can be performed over the phone on Cycle 2 Day 15 by research staff, if the participant is not able to physically attend to clinic.

Table 6: Required Activity Calendar

Tests and procedures	Screening	On trial						
		Prior to Registration	Cycle 1		Subsequent cycles		End of treatment	30-day post drug
			Day 1	Day 15	Day 1	Day 15		
Informed consent	X							
Inclusion/exclusion criteria	X							

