14.0 BIOSTATISTICS

As outlined in Table 1 Section 3, prior trials in patients with recurrent PCNSL have observed PFS6m of 35-45% with conventional chemotherapy regimens. The primary objective of this phase II study is to assess the efficacy of the targeted therapy buparlisib. PFS24w rate of patients receiving buparlisib will be estimated along with a 95% confidence interval. Progression-free survival at 24 weeks (PFS24w) is defined as the percentage of patients that have not developed progression of disease or died without progression at 24 weeks from the start of treatment. All patients will be followed for 6 months.

Twenty-one patients will be entered in this trial with an anticipated accrual rate of 1-2/months. The therapy will be considered worth pursuing if ≥ 12 out of 21 participants are progression free at 6 months (lower bound of the 95% confidence interval exceeds 34%, the approximate PFS24w rate with conventional chemotherapy).

Based on an accrual of 21 participants, two-sided 95% binominal confidence intervals for a range of overall response rate are as follows:

Table 14: Two-sided 95% binominal confidence intervals

Number of participants with overall response:		6	8	10	12	14	16
Point estimate of overall response rate:		29%	38%	48%	57%	67%	76%
Two-sided 95% confidence interval (exact binominal):	lower	11.28%	18.11%	25.71%	34.02%	43.03%	52.83%
	upper	52.18%	61.56%	70.22%	78.18%	85.41%	91.78%

In the unlikely event a patient is lost to follow-up before assessment of the primary endpoint he or she will be considered an event in the analysis of the primary endpoint.

In addition to PFS24w, we will assess progression-free survival at 12 weeks and 48 weeks (PFS12w and PFS48w). PFS12w/PFS48w is defined as the percentage of patients that have not developed progression of disease or died without progression at 3/12 months from the start of treatment. PFS12w and PFS48w rates of patients receiving buparlisib will be estimated along with a 95% confidence interval. The PFS12w will be assessed based on the

MEMORIAL SLOAN-KETTERING CANCER CENTER IRB PROTOCOL

IRB#: 14-177 A(5)

imaging and/or CSF assessment at day 1 cycle 3. PFS24w will be based on the imaging and/or CSF assessment at day 1 cycle 6, and PFS48w on imaging and/or CSF assessment at day 1 cycle 12.

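### Section 14 reads the primary PFS24w at day 1 of cycle 6, which is week 20 and has no scheduled scan, while the 12-of-21 rule is set against a 24-week rate

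*Combined protocol and SAP*

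**What the plan says.** Section 14 defines PFS24w as "the percentage of patients that have not developed progression of disease or died without progression at 24 weeks from the start of treatment" and sets the decision: "The therapy will be considered worth pursuing if ≥ 12 out of 21 participants are progression free at 6 months". The justification is that the lower limit of the exact 95% interval for 12/21 lies above 34%, described there as the approximate PFS24w rate with conventional chemotherapy. For the visit, "PFS24w will be based on the imaging and/or CSF assessment at day 1 cycle 6". The same sentence group ties PFS12w to day 1 of cycle 3 and PFS48w to day 1 of cycle 12.

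Section 9.0 fixes a cycle at 28 days, and Section 9.1 keeps the cycle count running during drug holds. Section 10.1 requires imaging and/or CSF "on all patients on day 1 cycle 3, and each additional odd numbered cycle (+/- 4 days"). Table 6, notes 2 to 4, repeats the odd-cycle schedule and adds an assessment at end of treatment.

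On scoring, Section 14 says "All patients will be followed for 6 months" and that if "a patient is lost to follow-up before assessment of the primary endpoint he or she will be considered an event". Section 12.8 defines PFS as a time-to-event variable shown by Kaplan-Meier. For a patient not known to have progressed or died at the cut-off or when further therapy starts, "PFS is censored at the time of the last tumor assessment before the cut-off date and before the anti-cancer therapy date". It rests PFS on the investigator's "assessment of MRI, CSF studies and clinical presentation".

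**The concern.** The assessment that decides the primary endpoint is named at a visit where the schedule provides none, and that visit is four weeks short of the landmark. Staff following the schedule will have a scan at week 16 and another at week 24, and Section 14 points to neither. If status is read at week 20, or carried from the week 16 scan because nothing newer exists at cycle 6, patients who fail between then and week 24 may count as successes. The comparison is still with a 24-week rate. The error runs in one direction, towards a positive result, in a single-arm trial whose only protection is that fixed rate.

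A smaller gap sits beside it. A binomial count needs a yes or no for each of the 21 patients. Section 14 names progression, death and loss to follow-up as failures. It does not say how to score a patient who starts other anti-cancer therapy without progression, or one who is in contact but has no assessment at the landmark. If that is settled after the data are seen, a result at the cut-off can depend on the choice.

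**Working it through.** **1. The plan's own figure.** The exact (Clopper-Pearson) lower 95% limit is the 2.5% quantile of Beta(x, n − x + 1). For 12/21 it is 34.02%, as in Table 14; the other five columns of that table also reproduce. For 11/21 it is 29.78%, so 12 is the smallest passing count. At a true rate of 34%, P(X ≥ 12) with X ~ Bin(21, 0.34) is 0.0249.

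**2. Visit timing.** Day 1 of cycle c is study day 28 × (c − 1) + 1, which is 4 × (c − 1) weeks after start.

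| Visit (day 1) | Study day | Weeks after start | Imaging/CSF scheduled | Used in Section 14 for |
|---|---|---|---|---|
| Cycle 3 | 57 | 8 | yes | PFS12w |
| Cycle 4 | 85 | 12 | no | – |
| Cycle 5 | 113 | 16 | yes | – |
| Cycle 6 | 141 | 20 | no | PFS24w |
| Cycle 7 | 169 | 24 | yes | – |
| Cycle 12 | 309 | 44 | no | PFS48w |
| Cycle 13 | 337 | 48 | yes | – |

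All three mapped visits fall four weeks before their landmark, and two of them have no scheduled assessment.

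**3. Effect on the decision.** Assume a constant hazard, a true 24-week rate of 34%, and that no event after the visit used is counted. The rate at week w is 0.34^(w/24).

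- Week 24: 34.0%; P(≥12/21) = 2.5%.
- Week 20: 0.34^(20/24) = 40.7%; P(≥12/21) = 9.6%.
- Week 16: 0.34^(16/24) = 48.7%; P(≥12/21) = 29.0%.

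Only patients with an event between the visit used and week 24 can change class. The expected number is 21 × (0.407 − 0.340) = 1.4 from week 20 and 21 × (0.487 − 0.340) = 3.1 from week 16.

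**4. Scoring of unresolved patients.** Start from exactly 12 counted successes, one of whom is unresolved. Scored as progression-free the result is 12/21, lower limit 34.02%, a pass. Scored as an event it is 11/21, 29.78%, a fail. Leaving the patient out would give 11/20, 31.53%, but no section proposes that.

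The documents give no expected number of such patients. With m of them and the other 21 − m at a true 34%, P(≥12/21) is:

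- all scored as events: 1.5% (m = 1), 0.9% (m = 2);
- all scored as progression-free: 4.3% (m = 1), 7.3% (m = 2);
- one patient who switched therapy, scored by observed status at an assumed 30% to 62.5% (the range of 6-month PFS values in Table 1, illustration only): 2.4% to 3.3%.

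At an assumed true rate of 60%, P(≥12/21) is 69.1%. It falls to 59.6%, 48.8% or 37.4% with one, two or three patients scored as events. With one switcher scored by observed status over the same range it is 64.4% to 69.5%.

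**The case against.** **On the visit.** Cycles 3, 6 and 12 end at weeks 12, 24 and 48 (3 × 4, 6 × 4, 12 × 4), so the author may have meant the end of those cycles. The definition in Section 14 runs to 24 weeks, and Section 12.8 admits clinical presentation. An event at week 22 can therefore still be counted, and a team that uses the cycle 7 scan would lose nothing. This stands as a limit on size: the 9.6% and 29.0% assume that all later events are ignored. It does not remove the point, because the text says day 1 and the schedule has no assessment there. A reader might also infer that the mismatch alters every patient's status. It does not: a patient who progresses before the visit used, or who is still progression-free at week 24, is classified the same way.

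**On scoring.** Three stronger readings are tempting.

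- That Sections 12.8 and 14 contradict each other on censoring. Section 12.8 attaches censoring to a time-to-event variable shown by Kaplan-Meier, and Section 14 defines a separate proportion with a fixed denominator. Both can stand.
- That an in-contact patient without a landmark assessment is progression-free by the wording of Section 14. That section also bases PFS24w on an assessment, so the patient is undefined. The 4.3% and 7.3% hold only under the less favourable reading. The group is also narrow: Section 9.1 keeps evaluations going during drug holds, Sections 12.2 and 12.3 already make clinical worsening a progression, and Table 6 schedules an assessment at end of treatment.
- That stable switchers must be failures. Scoring them by observed status is a coherent treatment-policy choice and barely moves the error in the illustration (2.4% to 3.3% against 2.5%). Scoring them as failures costs power. The Table 1 rates behind that range run from the start of salvage therapy, so they only approximate what a stable switcher faces between the switch and week 24.

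**Conclusion.** The visit error holds as written. Section 14 ties the primary endpoint to week 20, where no imaging or CSF is scheduled, and judges it against a 24-week rate. The direction favours the drug. The size lies between no effect (all events to week 24 counted) and a chance of wrongly passing of 9.6% (week 20) or 29.0% (week 16 scan carried forward), against 2.5% by design. Those upper figures rest on a constant hazard, a true 24-week rate of 34% and no later event counted. The PFS48w visit has the same fault. The PFS12w visit has a scan, but at week 8.

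The scoring gap is real but minor. It probably concerns few patients and matters mainly at 11 or 12 successes. The documents call for a stated rule. They do not support the claim that Section 12.8 censoring enters the count, or that one particular scoring of switchers is correct.

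**What to change.** 1. In Section 14, base PFS24w on the existing day 1 cycle 7 assessment (day 169, week 24, ± 4 days) and PFS48w on day 1 of cycle 13 (week 48).
2. Reconcile the PFS12w visit: cycle 3 is week 8, and no scan is scheduled at week 12.
3. State that Section 12.8 censoring applies to the Kaplan-Meier curve. Before the data are read, state how the count scores (a) a patient who starts other anti-cancer therapy without progression and (b) a patient in contact without a 24-week assessment. Report the number in each group and the count under the alternative scoring.
4. For (b), scoring a patient with no assessment at or after week 24 as an event would extend the existing loss-to-follow-up rule. A later scan without progression should count as progression-free at week 24. For (a), the scoring is the sponsor's choice. Whether local radiotherapy counts as other anti-cancer therapy has to be reconciled between Sections 11.10.5 and 11.10.8.1 first; no position is taken here.

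The cost is corrected visit references, a scoring sentence and one sensitivity line. The two corrected visits use scans already in the schedule. The count will be slightly less favourable than one read at week 20 or week 16, and any rule that scores unresolved patients as events carries the power loss shown above.

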12.9 Duration of response

Duration of response is defined as the time from the date of first occurrence of CR or PR to the date of the first documented PD or death due to any cause. If a patient is not known to have progressed or died at the date of the analysis cut-off or when he/she receives any further anti-cancer therapy, duration of response is censored at the time of the last tumor assessment before the cut-off date and before the anti-cancer therapy date.

Duration of response will be described using Kaplan-Meier curves with appropriate summary statistics.

13.0 CRITERIA FOR REMOVAL FROM STUDY

Duration of therapy will depend on individual response, evidence of disease progression and tolerance. The absence of treatment delays due to adverse events, treatment may continue until one of the following criteria applies:

- Disease progression
- Intercurrent illness that prevent further administration of treatment
- Unacceptable adverse event(s)
- Participant decides to withdraw from the study
- General or specific changes in the participant's condition render the participant unacceptable for further treatment in the opinion of the treating investigator.

The participant will be removed from study treatment when any one of the criteria listed above applies. The reason for study treatment removal and the date the participant was removed must be documented in the study-specific case report form. Alternative care options will be discussed with the participant.

In the event of unusual or life-threatening complications, investigators must immediately notify the Principal Investigator.

**MEMORIAL SLOAN-KETTERING CANCER CENTER
IRB PROTOCOL**

IRB#: 14-177 A(5)

Patients will be treated until disease progression, death, unacceptable toxicity or other discontinuation criteria are met.

After patients are removed from the trial they will represent after 30 days for a clinical follow-up visit. Thereafter, they will be followed for 12 months. The frequency of clinical follow-up visits is at the discretion of the investigator but we recommend a frequency of every 3-4 months. Thereafter, patients will be contacted over the telephone once a year.

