9.2 Treatment interruption and treatment discontinuation

If the study drug is being held due to toxicity, scheduled visits and all assessments should continue to be performed, with the exception of the dosing of the held study drug. If treatment with the study drug is withheld for ≥ 28 days, then the study drug must be permanently discontinued. Patients who permanently discontinue the study drug should have a follow up at approximately 30 days after discontinuation of all study treatment or resolution of the adverse event to \leq grade 1, whichever occurs first, that includes all study assessments appropriate to monitor the event.

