History, Physical and neuroexam	X	X		X		X	X	
Vital signs (blood pressure, pulse, respiration rate, temperature, height, weight) and KPS (Appendix 6)	X	X		X		X	X	
Serum pregnancy test (if applicable)	X	X		X		X		
Adverse event assessment	X			X		X	X	
Hematology group (CBC & diff)	X	X	X	X	X	X		
Chemistry group (Sodium, Potassium, Calcium, AST, ALT, Alk Phos, Total Bilirubin, Glucose, Creatinine)	X	X	X	X	X	X		
Fasting plasma glucose	X	X	X	X	X	X		
Coagulation (PT, PTT, INR)	X	X		X		X		
HbA1c	X							
8h fasting C-peptide	X							
Lipid panel	X			X*				
Amylase, lipase	X					X		
LDH	X							
Hepatitis B and C screen	X							
12-lead EKG	X			X ^s				
Chest X-ray				X ^s				
MUGA/ECHO	X							
HIV screen	X							
Bone marrow aspirate and biopsy	X							
PET brain and body	X							
PHQ-9 Patient self-rating mood scale	X		X	X	X (1)	X		
GAD7 Patient self-rating mood scale	X		X	X	X (1)	X		
NANO Score Assessment	X			X ^s		X		
Cerebrospinal fluid (CSF) Analysis including cytology	X			X(2)		X(2)		
Contrast-enhanced MRI/CT of the brain and total spine with perfusion	X			X(3)		X(3)		
Response evaluation				X (4)		X		
Computed tomography of chest, abdomen, pelvis	X							
Ophthalmologic evaluation including slit lamp exam	X							
PK BKM120 CSF			X(5)					
PK BKM120 Blood			X(6)					
Blood collection for genomic DNA			X					
Collection of archival FFPE tumor samples	X						X(7)	

- (1): PHQ-9 and GAD7 will be collected on day 15 of cycle 1 and day 1 and day 15 during cycle 2; then only on day 1 on subsequent cycles
 (2): Collection on day1 of all odd cycles starting on cycle 3; for patients with CSF disease only; response to treatment will be measured in CSF (+/- 4 days)
 (3): Imaging on day 1 of all odd cycles starting with cycle 3; MRI brain for patients with brain disease, MRI total spine for patients with intraspinal disease; MRI brain and total spine for patients with brain and spine disease as well as leptomeningeal disease (+/- 4 days)
 (4): Response will be evaluated on day 1 of all odd cycles starting with cycle 3
 (5): Patients with Ommaya reservoir: CSF collection at 1h, 2h, 4h after drug administration; no Ommaya: CSF collection through

lumbar puncture 2h after drug administration (+/- 30 min)

(6): Patients with Ommaya reservoir: Blood collect parallel to CSF collection at 1h, 2h, 4h after drug administration; no Ommaya: blood collection parallel to CSF collection through lumbar puncture 2h after drug administration (+/- 30 min)

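### No tumour imaging or CSF assessment is scheduled between the end-of-treatment visit and week 24 for patients who stop buparlisib without progression

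*Combined protocol and SAP*

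**What the plan says.** Section 14 sets the decision rule: "The therapy will be considered worth pursuing if ≥ 12 out of 21 participants are progression free at 6 months", with the condition "lower bound of the 95% confidence interval exceeds 34%, the approximate PFS24w rate with conventional chemotherapy". It bases PFS24w on an imaging and/or CSF assessment at a named treatment-cycle visit. It counts a patient lost to follow-up before that assessment as an event. It also states "All patients will be followed for 6 months", without naming any tumour assessment.

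Table 6 (Section 10.1) enters MRI/CT, CSF and response evaluation under on-treatment cycles and end of treatment, with MRI/CT and CSF also at screening. Note 3 reads "Imaging on day 1 of all odd cycles starting with cycle 3". None of the three has an entry in the 30-day post-drug column.

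Section 9.2 covers temporary holds: "If the study drug is being held due to toxicity, scheduled visits and all assessments should continue to be performed". After permanent discontinuation it asks for a follow-up at about 30 days or at resolution of the event, with assessments suited to monitoring that event. Sections 9.1 and 10.3 require patients stopped for an adverse event to be followed at least weekly for 4 weeks, then every 4 weeks until resolution or stabilization. Section 13 adds a 30-day clinical visit, then 12 months of clinical visits: "The frequency of clinical follow-up visits is at the discretion of the investigator but we recommend a frequency of every 3-4 months". Yearly telephone contact follows.

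Section 12.8 bases PFS on MRI, CSF and clinical presentation. It censors a patient not known to have progressed or died at the last tumour assessment.

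**The concern.** Section 13 lists adverse events, intercurrent illness and withdrawal as reasons for ending treatment separate from progression, so stopping without progression before week 24 is foreseeable. Such a patient has an end-of-treatment scan and then, if the plan is followed exactly, no further scheduled MRI or CSF. The plan asks for a binary 24-week status for all 21 patients but does not collect the assessment on which that status is to be based.

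The scoring of such a patient is then open. Counting the patient progression-free may credit an undetected progression. Counting the patient as an event may discard a true success. Scanning at the investigator's discretion would let ascertainment differ between patients in an open-label trial with investigator-assessed outcome. PFS48w has the same gap.

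**Working it through.** **Inputs.** From Section 14: n = 21, a go at 12 or more progression-free, and a reference rate of 34%. No alpha, power or target rate is stated; the two-sided 95% interval implies one-sided 0.025. Assumptions: a favourable true rate of 57% (the point estimate at 12/21), and k = 1 to 4 patients without a week-24 tumour assessment.

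**Step 1: the plan's own figure.** The exact (Clopper-Pearson) 95% interval for 12/21 is 34.02% to 78.18%, as in Table 14; the other five columns also reproduce. For 11/21 the interval is 29.78% to 74.29%. The rule is met by 0.02 percentage points at 12 and fails at 11, so one patient's status can decide the trial.

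**Step 2: the rule with every patient assessed.** P(X ≥ 12), X ~ Bin(21, p): 0.0249 at p = 0.34 and 0.586 at p = 0.57.

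**Step 3: k patients unassessed.** The other 21 − k patients are independent with true rate p.
- Counted progression-free: go if X ≥ 12 − k, with X ~ Bin(21 − k, p).
- Counted as events: go if X ≥ 12, with X ~ Bin(21 − k, p).

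| k | False go at p = 0.34, counted progression-free | Chance of go at p = 0.57, counted as events |
|---|---|---|
| 0 | 2.5% | 58.6% |
| 1 | 4.3% | 48.6% |
| 2 | 7.3% | 38.2% |
| 3 | 12.0% | 28.1% |
| 4 | 18.8% | 18.9% |

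Excluding the unassessed patients would move the cut-off to 12/20, 12/19, 11/18 or 11/17 for k = 1 to 4, which the plan does not provide for.

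**Step 4: which rule applies to a patient who is seen but not scanned?** The lost-to-follow-up rule does not, because the patient is still followed. Section 12.8 would censor at the last tumour assessment, which gives no binary status. Sections 12.8 and 14 therefore do not settle the count.

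**Step 5: the named visit.** With 28-day cycles, day 1 of cycle c falls at 4(c − 1) weeks. Day 1 of cycle 6, which Section 14 names for PFS24w, is week 20 and not an odd-cycle imaging visit. Day 1 of cycle 7 is week 24 and is on the imaging calendar.

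**The case against.** A reader might infer that 24-week status is never measured in these patients. The documents do not support that. Sections 12.2 and 12.3 count clear clinical worsening, and failure to return because of death or deterioration, as progression. Section 12.8 admits clinical presentation, and adverse-event stoppers are seen weekly and then 4-weekly until resolution or stabilization. Section 3.3 describes a rapid clinical course after relapse, so many progressions would show themselves. Later scans are not forbidden; they are simply not scheduled.

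The lost-to-follow-up rule also points towards conservative scoring. Since Section 14 requires imaging and/or CSF for PFS24w, an unscanned patient has weak support as a success, which makes the false-go column the less likely reading.

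The false-go figures are upper bounds. Suppose stoppers are progression-free at week 10 and the hazard is constant (both assumptions). At a true 34%, such a patient is still progression-free at week 24 with probability 0.34^(14/24) = 0.53. If a fraction q of all patients stops in this way, the apparent rate when they are counted as successes is 0.34 + q(1 − 0.53). For q = 10% and 20% this gives false-go rates of 6.7% and 14.6%, lower still if some progressions show clinically. The same reasoning deepens the loss when they are counted as events: at a true 57%, the chance of a go falls to about 33% and 13%.

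Two further inferences fail. The 10-30% rate of grade 3-4 liver events in Section 11.11.1 is not a discontinuation rate: it is regardless of drug relationship, and Table 11 does not require a permanent stop for every grade 3 event. Duration of response is not left to guesswork, because Section 12.9 censors it at the last tumour assessment; the gap makes that censoring early.

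What stands: none of these texts schedules a scan or CSF sample after end of treatment, and the six-month follow-up statement does not add one.

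**Conclusion.** The gap holds in a limited form. For patients who stop without progression, the plan schedules no MRI or CSF between end of treatment and week 24, so silent progression, or its absence, goes unrecorded for an endpoint that Section 14 defines by those assessments.

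The size depends on k, which the documents do not give. For k = 1 to 4, the bounds are a false-go rate of 4.3-18.8% instead of 2.5% at a true 34%, or a chance of a go of 49-19% instead of 59% at a true 57%. They assume that all k patients are scored the same way and that the rest have the stated true rate. Even k = 1 matters, because the rule turns on a single patient. The trial is exploratory, but this is its only primary endpoint and decision rule, and assessments not made by week 24 cannot be recovered later.

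**What to change.** In Section 13 and Table 6, state that patients who stop buparlisib without progression keep the existing 8-weekly MRI and/or CSF assessments, on the original calendar from treatment start, until progression, death, new anti-cancer therapy or week 48, and at minimum through week 24.

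In Section 14:
- State that a patient with no week-24 tumour assessment, including one who starts new anti-cancer therapy earlier, counts as an event for the binary PFS24w endpoint.
- Reconcile this with the censoring rule in Section 12.8, which can remain for the Kaplan-Meier analysis.
- Tie PFS24w to a visit on the imaging calendar; day 1 of cycle 7 is week 24.

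The scoring rule alone is not enough. It makes the count determinate, but at the loss of power shown above, so continued assessment should keep the number of unassessed patients small.

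The cost is a protocol amendment and a few off-treatment scans or CSF samples in a small number of patients. Section 17.0 charges the patient or insurer for everything except study drug and exploratory analyses, so the amendment must say who pays for these assessments.
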